## I. GENERAL INFORMATION

Reception stamp

1. **Date of application:** July 31, 2011
2. **Project name (English title):** TARGIT-BQR (TARGEted Intraoperative RadioTherapy – Boost Quality Control Registry)
3. **Is this a multicenter study?** Yes:  No:
4. **Specify type of study:** Quality assurance according to radiation protection guidelines

Pilot study? Comparative? Placebo? Open? Randomized? Single-blind? Double-blind?

5. **Name and address of the responsible study director in the field of medical EK II:**  

**7. Head of clinic or institute: [name]. [name]**

**8.0 Who is covering the costs of the study (please also indicate partial funding)? Not applicable**

**The expense allowance for the Medical Ethics Committee II for the assessment of the project will be covered by (provide billing address):** (only studies without any financial support are free of charge; see also the official fee schedule of the Ethics Committees of Heidelberg University)

**9.0 Has an application with the same content already been submitted to another ethics committee?**

No

a) If yes, when and where:

b) Has a vote already been cast (please enclose a copy):

**10. For multicenter study applications:**

**Has a positive vote been obtained from the project manager/study director (LKP) responsible for Germany?**

For multicenter studies, the vote of the responsible project manager/study director (LKP) must be available before the application can be assessed by the local ethics committee.

Mannheim Medical Ethics Committee as the leading EC

## **II. DESCRIPTION OF THE PROJECT**

**11. Aim of the study** (brief outline with the main objectives):

As part of quality assurance in accordance with radiation protection guidelines and X-ray regulations, radiation therapists are required to provide regular follow-up care after therapeutic radiation application. As a rule, annual follow-up examinations with structured documentation of local control and side effects take place for up to 5 years after the end of therapy.

Intraoperative radiotherapy has been performed for breast cancer as an early tumor bed boost for several years in accordance with national guidelines (Sautter-Bihl et al: DEGRO practical guidelines for radiotherapy of breast cancer. Strahlenther Onkol 2007; 183:661-666). We have already published several articles on the safety and toxicity of the procedure (e.g., Wenz F, Welzel G, Blank E, Hermann B, Steil V, Suetterlin M, Kraus-Tiefenbacher U: Intraoperative radiotherapy (IORT) as a boost during breast conserving surgery (BCS) using low kV X-rays – the first five years of experience with a novel approach. Int J Radiat Oncol Biol Phys 77:1309-1314, 2010).

As part of the project, a multicenter study will now be conducted to determine whether the results we have achieved can also be achieved in regional healthcare settings. To this end, patients who receive IORT as an early tumor bed boost and are treated and followed up in accordance with the guidelines will be prospectively registered and documented. For this purpose, pseudonymized data from the other centers will be faxed to the registry center in Mannheim and evaluated by us.

**12. Planned start and expected duration of the study:** September 1, 2011

**13. a) Examination of patients**

Number/inpatient:	1000
Number/outpatients:	0
Patients capable of giving consent	100
Patients unable to give consent	0

**b) Examination of test subjects:** Not applicable

Number:

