**17 a) Inclusion criteria for patients/subjects:**

- I. Are women of childbearing age included? Yes
- II. How is conception protection ensured, if applicable: Yes, standard under RT
- III. Are study participants who are incapable of giving consent included? No
- IV. Are underage study participants included? No

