**b) Exclusion criteria for patients/subjects:**

- I. Are women of childbearing age excluded? No
- II. Is drug abuse checked and how? No
- III. Are study participants who are incapable of giving consent excluded? Yes

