Targeted Intraoperative Radiotherapy Boost Quality Registry (TARGIT BQR)

Statistical Analysis Procedures – 09. December 2025

(NCT01440010)

PI: [name]; MD

Oncological Outcome

Outcome variables were local recurrence, ipsilateral breast carcinoma, contralateral breast carcinoma, local lymph node metastasis and distant metastasis. Kaplan-Meier estimates were done to calculate cumulative rates for disease-free survival, local recurrence rate, local recurrence-free survival, metastasis-free survival and overall survival. For all Kaplan-Meier estimates, death was also counted as an event and not censored, except for local recurrence rate where only recurrences were counted as an event. For disease-free survival any event (death, local recurrence, metastasis, ipsilateral breast carcinoma, contralateral breast carcinoma, local lymph node recurrence) was included whatever occurred first. Eight patients had bilateral breast cancer and were counted once in case of an event of metastasis or death. The statistical analysis was performed for the endpoints of the oncological outcome in an intention-to-treat-setting using SPSS, Version 27.

Toxicity

For cumulative toxicity rates grade 2 fibrosis, breast edema, lymphedema, hyperpigmentation, retraction, and pain were documented if they occurred at least 3 times during the follow-up period. Teleangiectasia and ulceration, irrespective of their severity, were recorded as single occurrences. Data on acute and long-term toxicity were recorded. Simple frequencies, relative and absolute values, and cumulative rates were calculated. Cumulative rates were calculated based on the Kaplan-Meier method (SAS, release 9.3 and SPSS, Version 27). This is an intention-to-treat-analysis of the whole cohort. All data were collected at the study center in Mannheim. The registry closed recruitment in December 2020.

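### Does the entry of 100 consent-capable patients in item 13 a) of the protocol contradict the planned 1000 patients?

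*Protocol*

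**What the plan says.** Item 13 a) of the protocol, an ethics application dated July 31, 2011, has four entries. Two give the planned size by care setting: "Number/inpatient: 1000" and "Number/outpatients: 0". Two describe capacity to consent: "Patients capable of giving consent 100" and "Patients unable to give consent 0". The first pair is labelled as numbers; the second pair has no such label and no unit.

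Item 13 b) brings in no second group: "b) Examination of test subjects: Not applicable".

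Item 17 deals with capacity to consent twice. Under inclusion: "Are study participants who are incapable of giving consent included? No". Under exclusion: "Are study participants who are incapable of giving consent excluded? Yes".

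The SAP, dated 09 December 2025, states no planned or analysed total. Its toxicity section describes an analysis of the whole cohort and ends with "The registry closed recruitment in December 2020".

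**The concern.** The four entries stand in one list, and the first two are plainly head counts. A reader who carries that unit down the list finds two totals for the same patients: 1000 by care setting and 100 by capacity to consent. Item 17 sharpens the mismatch, because if nobody unable to consent is registered, the consent-capable row should equal the whole planned number.

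Two things could be at stake. This is the place where the ethics committee is told how many patients take part and how many of them can consent, so a tenfold discrepancy there would be awkward. It is also the only place in the two documents that gives a planned size. If the figures truly conflict, one could ask whether 1000 is itself right.

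**Working it through.** **Inputs.** From item 13 a): inpatients I = 1000, outpatients O = 0, consent-capable entry 100, consent-unable entry 0. From item 13 b): no test subjects. From item 17 a) III and b) III: no registered patient is unable to consent.

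**Planned total by setting.** N = I + O = 1000 + 0 = 1000.

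**What the consent rows must satisfy.** Let C be the number able and U the number unable to consent. Every patient is one or the other, so C + U = N. Item 17 forces U = 0, hence C = N. As a share of N, that is 100% able and 0% unable, whatever N is.

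**Check under each reading.**

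| Reading of the consent rows | C + U | Total by setting | Gap |
|---|---|---|---|
| Counts as printed | 100 + 0 = 100 | 1000 | 900 |
| Percentages | 100% of 1000 + 0% of 1000 = 1000 | 1000 | 0 |
| Counts, a zero dropped from 100 | 1000 + 0 = 1000 | 1000 | 0 |
| Counts, a zero too many in 1000 | 100 + 0 = 100 | 100 | 0 |

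On the literal count reading, 100/1000 = 10% of patients are classified and 900/1000 = 90% are not.

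**Weighing the readings.** The literal count reading needs 900 patients who neither can nor cannot consent, which is impossible. The third and fourth readings each need a digit error in a printed figure. The percentage reading needs no wrong digit, only an unprinted or lost sign. It also fits three features of the text: the rows lack the number label, the two entries sum to exactly 100, and 100% with 0% is what item 17 implies. It is the simplest reading, although the documents do not prove it.

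**Does anything downstream use the entry?** The documents contain no power calculation, no precision target and no decision rule. The SAP specifies Kaplan-Meier estimates for the oncological endpoints, and frequencies and cumulative rates for toxicity. None of these takes 100 or 1000 as an input.

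**Least favourable case.** Suppose the planned total had really been 100. With standard errors scaling as 1/√n, the precision expected at planning would have been worse by a factor of √(1000/100) = √10 ≈ 3.16. Even so, the width of the reported intervals depends on the patients and events actually recorded, and no planned precision exists against which to judge it. The effect on the analysis is therefore zero under all four readings.

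**The case for a change.** The strongest case for acting is that an ethics application should be readable in only one way. The consent rows follow directly on two rows of counts with no marked change of unit, and as counts they do not add up. Nothing in the supplied text shows that a sign was lost. The percentage reading is an inference, and an extra zero in 1000 would reconcile the entries too. A clarifying line would cost almost nothing.

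Part of this stands. The unit is not printed in the text available, the entries do not reconcile as counts, and the documents do not settle which reading was meant.

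The step from there to a defect in the plan does not stand. The form states no sum that fails; the mismatch appears only once the reader supplies the unit of persons, which item 17 rules out for the figures as printed. If the source form carries a percentage sign, there is nothing to correct at all. The substantive question, whether every registered patient must be able to consent, is answered without ambiguity by item 17. The doubt about an extra zero concerns a planned size that no analysis uses, and recruitment has ended. Cheap as a note would be, it would change nothing for patients, data or results.

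**Conclusion.** The concern does not hold as an arithmetic error. Item 13 a) has a clerical ambiguity about the unit of two entries: the gap to the planned total is 900 if they are literal counts and 0 if they are percentages. The percentage reading is the most natural one and agrees with item 17. The effect on every planned estimate, interval and conclusion is nil, so no change to the plan follows.

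This rests on two things. First, item 17 is taken at face value: no patient unable to consent is registered. Second, neither document uses the planned size in any calculation or rule, which is so in the text supplied. The conclusion does not depend on which reading is right. Two points stay open: what the source form prints beside the two entries, and independent confirmation of the planned total of 1000. Neither can be settled from these documents, and neither bears on the analysis.

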**14. Expected duration of the study phase for each patient/subject: 5 years**

**15. Age of patients/subjects:**

Lower limit: 18 years  
Upper limit: 85 years

**16. What exactly will be done with the patient/subject?**

Detailed description requested. Additional measures that are purely study-related must be clearly indicated.

What is the ratio of the expected benefits of the study to the risks associated with it?

The patient receives standard therapy and follow-up care in accordance with guidelines. No additional imaging examinations or blood samples are taken. The standard documentation is faxed to us and evaluated by us.

**16.1 Purely study-related measures on patients/subjects that would not otherwise be necessary, e.g.:**

Inpatient stay	No
Blood samples: quantity, number of samples, timing	No
Bladder catheter	No
Endoscopy	No
Biopsies, other tissue sampling	No
Lumbar puncture, amount of cerebrospinal fluid	No
X-ray diagnostics	No
Computed tomography	No
Magnetic resonance imaging	No
Positron emission tomography	No
Radioactive substances/tracers	No
Other invasive measures	No

**17 a) Inclusion criteria for patients/subjects:**

- I. Are women of childbearing age included? Yes
- II. How is conception protection ensured, if applicable: Yes, standard under RT
- III. Are study participants who are incapable of giving consent included? No
- IV. Are underage study participants included? No

**b) Exclusion criteria for patients/subjects:**

- I. Are women of childbearing age excluded? No
- II. Is drug abuse checked and how? No
- III. Are study participants who are incapable of giving consent excluded? Yes

**18. Is this a**

- trial under the Medical Devices Act (MPG)? No  
If "yes," then the application must be submitted via DIMBI.  
If there is a CE mark, the intended purpose is identical, and no invasive or stressful examinations are carried out for the purposes of the study, § 23b MPG applies and you can proceed with this application.
- Trial to which the X-ray Ordinance applies: No
- Experiment to which the Radiation Protection Ordinance applies: No
- **Experiment in which genetic information is determined:** No

**19. Does the research involve human tissue? No**

Has consent been obtained regarding the origin of the tissue?  
Is it possible to trace the tissue back to the donor?

**20. Is this research involving human genetic material? No**

**20.1 Does the data protection concept for this study meet the requirements of the European research project "Advanced Clinico Genomic Trials on Cancer (ACGT; [www.eu.acgt.org](http://www.eu.acgt.org) or [www.privacypeople.org](http://www.privacypeople.org))?" Yes**

**21 If the general requirements for clinical trials pursuant to Section 23b MPG are met, proof of the CE mark must be provided.**

**Not applicable**

**22 If the study**

- directly in the interests of patients: No
- a purely scientific purpose without direct diagnostic and therapeutic value for patients: yes
- the future development of diagnostic and therapeutic procedures: yes
- the acquisition of knowledge about the causes and prognosis of diseases: no
- Gaining insights into specific issues relating to the health status of the population: No
- Other objectives: Yes, comprehensive quality assurance

**23. What typical side effects or complications can be expected?**

No study-related measures

**24. Are there any risks for the subjects/patients? No**

If yes, which ones:

**25. To what extent does the study place an additional burden on subjects/patients?**

Not applicable, as only additional documentation is required.

**26. Are those involved proficient in the techniques to be used? Yes**

**27. How can complications be recognized and treated? Not applicable**

**27. Type and frequency of planned monitoring measures before, during, and after the examination period? According to guideline**

28. Is there insurance coverage and for whom (study participants or investigator)?

**Not applicable**

### Type of insurance:

## 28.1 Where study participants are insured

## Subject insurance analogous to the insurance required by law in the German Medicines Act (AMG) and Medical Devices Act (MPG) for high-risk projects

Coverage must be confirmed and the insurance provider must be based in the Federal Republic of Germany.

**Accident/travel insurance for test subjects/patients; additional or standalone**

The German Medical Association (Ethik-Kommission II) recommends such insurance for test subjects and patients who are examined at other locations or who have to travel for study purposes, provided that no other insurance cover exists for this.

**28.2 In which the employees of the University Hospital GmbH (UMM), the Central Institute for Mental Health, or the Medical Faculty involved in the study are insured against liability claims by study participants (hospital liability insurance – research and teaching sector)**

### 28.3 Other type of insurance, which?

### Details of the insurance provider:

Name of the insurance provider, full address including telephone and fax number,  
Policy number: (Please enclose a copy of the contract)

**28.4 Were the study participants informed of the insurance obligations in the patient/subject information, or is a copy of the obligations provided?**

**Not applicable**

29 Is the clinical trial investigator informed about the results of the technical safety assessment of the investigational products and the anticipated risks associated with the clinical trial? Yes

30 Have similar or comparable projects already been carried out or are they currently being carried out?

If so, with what results? Yes, single-center, see publication, high safety and low toxicity rate

### 31. For other studies:

For other studies: Are there any doubts as to whether the project complies with the Declaration of Helsinki 1964, as revised in 1996? No

### III. Information, explanation, consent. Federal Data Protection Act

The Ethics Committee II of the Medical Faculty of Heidelberg University is of the opinion that the processing of the initials and/or full date of birth of a trial participant does not constitute pseudonymization of health data within the meaning of Section 2a (2) sentence 2 no. 1 b)-d) AMG in conjunction with § 3 (6a) Federal Data Protection Act (BSOS) and is therefore unauthorized within the meaning of § 43 (2) No. 1, possibly in conjunction with § 44 (1) BDSG.

32. Does the written subject/patient information presented here correspond to the final version (in the case of multicenter studies, the latest and approved version of the ethics committee responsible for the LKP)? Yes

33. Patient or subject information and the declaration of consent should be written in a single document with consecutive page numbers and must be signed by the person providing the information and the study participant at the end of the document.

34. Is the patient information and consent form marked with a current version number and date in the footnote? Yes

35. Has an information sheet appropriate for the age group been created for the participation of minors? Not applicable

36. Has the patient/subject information sufficiently addressed and clearly indicated other, alternative treatment methods?

Not applicable

37. Has the privacy policy been adapted to the individual study conditions? Yes

38. Is the section on data protection integrated into the patient/subject information and highlighted by a frame or bold print? Yes

39. Has the method of pseudonymization been described in an understandable manner and does it ensure data protection in accordance with legal requirements (Federal Data Protection Act §3, para. 6)? Is the section on data protection sufficiently detailed and understandable to laypersons? Yes

40. Who provides clarification? Treating physicians

41. If the patient's capacity to make decisions could be called into question, who objectively assess the patient's capacity to make decisions? Not applicable

42. Has consideration been given to the possibility that a legal guardian for the patient may be required? Not applicable

#### IV. **Final Check**

*Does the patient information and consent form meet the standard criteria?*

- Does the patient information and consent form have a version number?
- Have the latest proposed changes been implemented and marked (bold, italics, etc., is this the final version)?
- Is it headed with the name of the investigating clinic and the responsible investigator?
- Is the insurance provider named, including the policy number and full address?
- Are all topics covered in the patient information? (see sample texts)
- Does the declaration on confidentiality, data processing, and data protection comply with legal requirements?
- Are all medical terms translated in a way that is understandable to laypeople?
- Is a contact person for the study participant named and contact details provided in the patient information?
- Has the study participant been expressly made aware of the insurance obligations, if applicable?
- Are the required signatures present?
- Is the phrase "the patient/subject has received a copy of the patient information and consent form" mentioned?
- Is there a reference to voluntariness, the possibility of withdrawal, etc.?

- Have the special circumstances of patients who are unable to give consent been taken into account?
- Have the currently valid X-ray regulations and radiation protection regulations been observed?

Targeted Intraoperative Radiotherapy Boost Quality Registry (TARGIT BQR)

Statistical Analysis Procedures – 09. December 2025

(NCT01440010)

PI: [name]; MD

Oncological Outcome

Outcome variables were local recurrence, ipsilateral breast carcinoma, contralateral breast carcinoma, local lymph node metastasis and distant metastasis. Kaplan-Meier estimates were done to calculate cumulative rates for disease-free survival, local recurrence rate, local recurrence-free survival, metastasis-free survival and overall survival. For all Kaplan-Meier estimates, death was also counted as an event and not censored, except for local recurrence rate where only recurrences were counted as an event. For disease-free survival any event (death, local recurrence, metastasis, ipsilateral breast carcinoma, contralateral breast carcinoma, local lymph node recurrence) was included whatever occurred first. Eight patients had bilateral breast cancer and were counted once in case of an event of metastasis or death. The statistical analysis was performed for the endpoints of the oncological outcome in an intention-to-treat-setting using SPSS, Version 27.

Toxicity

For cumulative toxicity rates grade 2 fibrosis, breast edema, lymphedema, hyperpigmentation, retraction, and pain were documented if they occurred at least 3 times during the follow-up period. Teleangiectasia and ulceration, irrespective of their severity, were recorded as single occurrences. Data on acute and long-term toxicity were recorded. Simple frequencies, relative and absolute values, and cumulative rates were calculated. Cumulative rates were calculated based on the Kaplan-Meier method (SAS, release 9.3 and SPSS, Version 27). This is an intention-to-treat-analysis of the whole cohort. All data were collected at the study center in Mannheim. The registry closed recruitment in December 2020.

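### The SAP gives no rule for deaths in the Kaplan-Meier toxicity rates; the natural reading censors them, which overstates each rate slightly, and cumulative incidence would fix it

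*SAP*

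**What the plan says.** The SAP has two paragraphs, Oncological Outcome and Toxicity.

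- **Oncological Outcome** first lists what is estimated: "Kaplan-Meier estimates were done to calculate cumulative rates for disease-free survival, local recurrence rate, local recurrence-free survival, metastasis-free survival and overall survival". The next sentence gives the death rule, "For all Kaplan-Meier estimates, death was also counted as an event and not censored", and one exception, "except for local recurrence rate where only recurrences were counted as an event".
- **Toxicity** defines the events. Six grade 2 items "were documented if they occurred at least 3 times during the follow-up period". For the other two, "Teleangiectasia and ulceration, irrespective of their severity, were recorded as single occurrences". On method it says "Cumulative rates were calculated based on the Kaplan-Meier method", naming two software packages, and on population "This is an intention-to-treat-analysis of the whole cohort". It has no sentence on death.

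Neither document mentions competing risks or cumulative incidence. The protocol has no statistical section that could supply the missing rule. It sets 5 years of participation per patient (item 14) and an upper age limit of 85 (item 15), so some deaths during follow-up are to be expected.

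**The concern.** Side effects are one of the two things the registry exists to document (protocol item 11, alongside local control), and its benchmark is a single-centre experience described as having low toxicity (item 30). A reader of a five-year fibrosis or ulceration rate will take it as the share of treated patients who developed that toxicity.

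A Kaplan-Meier curve gives that share only if nobody dies first. When deaths are censored, the estimator treats women who died as still able to develop the toxicity later, at the same rate as survivors. The result is a hypothetical rate in a population without deaths, which the SAP does not claim to be estimating. Because the Toxicity paragraph is silent and the nearest rule uses the word all, a reader also cannot be certain from the text alone how deaths were coded.

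**Working it through.** **Nothing to reproduce.** The documents state no toxicity rate, death rate, power or precision. The check therefore compares estimators under assumed rates.

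**Inputs.** From the documents: 5-year horizon (protocol item 14), 1000 planned patients (item 13), Kaplan-Meier for toxicity (SAP, Toxicity). Assumed: constant hazards, five-year mortality of 5 to 10%, true five-year toxicity incidence of 1, 10 or 20%.

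**Formulas.** Let Lt and Ld be the five-year cumulative hazards of toxicity and of death.

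- Cumulative incidence, death competing: CIF = Lt/(Lt+Ld) × (1 − exp(−(Lt+Ld)))
- One minus Kaplan-Meier, death censored: A = 1 − exp(−Lt)
- One minus Kaplan-Meier, death as an event: B = 1 − exp(−(Lt+Ld))

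**Direction.** At each toxicity event, Aalen-Johansen adds (events/at risk) × the proportion alive and toxicity-free. Censored Kaplan-Meier adds the same fraction × a survival function that ignores deaths and so is never smaller. Hence CIF ≤ A ≤ B whatever the hazards. In 300 simulated cohorts of 1000 (toxicity 5% with death censored, mortality 10%), the mean estimates were 4.71%, 4.96% and 14.47%, and the ordering was never violated.

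**Worked case: true incidence 10%, mortality 10%.** Ld = −ln(0.90) = 0.1054. Solving CIF = 0.10 gives Lt = 0.1112.

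- Check: 0.1112/0.2166 × (1 − exp(−0.2166)) = 0.5135 × 0.1947 = 0.100
- A = 1 − exp(−0.1112) = 10.53%
- B = 1 − exp(−0.2166) = 19.47%

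**Results for 5% to 10% mortality.**

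| True incidence | Death censored (A) | Excess, points | Death as event (B) |
|---|---|---|---|
| 1% | 1.03 to 1.05% | 0.03 to 0.05 | 6.0 to 10.9% |
| 10% | 10.25 to 10.53% | 0.25 to 0.53 | 14.7 to 19.5% |
| 20% | 20.50 to 21.03% | 0.50 to 1.03 | 24.5 to 28.9% |

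Column A is about 2.5 to 5% too high in relative terms. On a wider grid (2 to 30% toxicity as measured by A, 3 to 15% mortality) the excess of A over CIF runs from 0.03 to 2.18 points, or 1.01 to 1.08 times.

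**Which column applies.** The death rule stands under Oncological Outcome, directly after the list of five estimates, and its single exception is a member of that list. The oncology paragraph closes with its own analysis-set and software statement, and the Toxicity paragraph then gives its own again. The SAP is written section by section, which points to column A.

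**The case against.** The strongest reply is that the effect is too small to matter. With 1000 patients, complete follow-up and simple binomial error, the 95% half-width is 1.96 × √(p(1−p)/1000): 0.62 points at 1%, 1.86 at 10% and 2.48 at 20%. The largest biases in the table (0.05, 0.53 and 1.03 points) lie inside these. The SAP also reports simple frequencies, which depend on no Kaplan-Meier death rule and would expose a badly distorted curve. The mortality and toxicity inputs are assumptions.

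Most of this stands, and it is why the point is minor. It does not remove the point. The bias always goes the same way and can be avoided at little cost. Simple frequencies do not allow for incomplete follow-up, so they cannot replace a correct cumulative rate. A death-censored rate could be defended as a deliberate no-death quantity, but the SAP does not say that is what it wants.

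A reader might go further and infer from the word all that deaths were counted as toxicity events, since toxicity is not excepted. That would put column B in force, with a 1% toxicity shown as 6.0 to 10.9%. The documents do not support this. The rule's position, the preceding list and the source of its exception tie it to the oncological estimates, and a curve counting deaths as ulceration would be clinically implausible. The wording leaves that reading open but does not show that it was followed.

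**Conclusion.** The SAP does not state how deaths are handled in the toxicity curves. On the natural reading they are censored, and the reported rates are then never below the cumulative incidence; they exceed it whenever toxicity events follow earlier deaths. Under constant hazards and an assumed five-year mortality of 5 to 10%, the overstatement is about 2.5 to 5% of the rate, at most about one percentage point for a toxicity of 20%. This is minor. The direction needs no assumption about hazards, but the size depends on mortality figures the documents do not give.

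The gross inflation of rare toxicities belongs only to the literal reading and is not an established consequence. It is a reason to make the wording unambiguous.

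The local recurrence rate raises the same issue without any doubt about wording: only recurrences count as events there and deaths are censored, so the same formulas and direction apply.

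**What to change.** 1. Reword the death rule so that it names the endpoints it covers: disease-free, local recurrence-free, metastasis-free and overall survival.
2. Add to the Toxicity paragraph that each toxicity rate is a cumulative incidence with death before the toxicity as a competing event (Aalen-Johansen), reported with a 95% CI at 5 years.
3. Use the same estimator and interval for the local recurrence rate.
4. State how deaths were coded in any toxicity curves already produced, so that the literal reading can be ruled out.

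No new data are needed. Recruitment closed in December 2020 and the SAP already estimates overall survival. The cost is a few lines of SAP text, a small amount of programming and a rerun of the affected curves.

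### The local recurrence rate censors deaths and so slightly overstates the actual probability of recurrence; a cumulative incidence should stand beside it

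*SAP*

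**What the plan says.** Under Oncological Outcome the SAP names one estimator for all its time-to-event results: "Kaplan-Meier estimates were done to calculate cumulative rates for disease-free survival, local recurrence rate", followed by local recurrence-free survival, metastasis-free survival and overall survival. The rule for deaths is "For all Kaplan-Meier estimates, death was also counted as an event and not censored", and one exception follows directly: "except for local recurrence rate where only recurrences were counted as an event". The exception is disclosed openly. The SAP does not describe the result as a rate with deaths censored, and it names no competing-risk method.

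Under Toxicity the SAP again uses this estimator: "Cumulative rates were calculated based on the Kaplan-Meier method". That section does not mention deaths.

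The Protocol's aim (item 11) is to find out "whether the results we have achieved can also be achieved in regional healthcare settings". It describes "annual follow-up examinations with structured documentation of local control and side effects take place for up to 5 years", and item 14 reads "Expected duration of the study phase for each patient/subject: 5 years". The SAP is dated December 2025 and records that "The registry closed recruitment in December 2020".

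**The concern.** When death is censored, Kaplan-Meier treats a patient who died without recurrence as someone who could still recur later. One minus the estimate then answers a hypothetical question: how many patients would recur if nobody died first. Even that reading needs death to be independent of recurrence, which the SAP does not state. A reader of a quality registry will more naturally take a cumulative local recurrence rate as the probability that a treated patient actually has a recurrence. The planned estimate can equal that probability or exceed it, but cannot fall below it.

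None of the other planned oncological estimates supplies the missing quantity. The complement of local recurrence-free survival adds deaths to recurrences. The simple frequencies that the SAP mentions are listed under Toxicity, not for local recurrence. At stake is how one reported figure is read; no test or decision in the plan depends on it.

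**Working it through.** **No figure to reproduce.** The documents give no recurrence rate, death rate, event count or sample-size calculation. The size below is an illustration.

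**Direction.** At each recurrence time, Kaplan-Meier with deaths censored adds S_R × d/n, where S_R is the running product over recurrences only. Aalen-Johansen adds S_all × d/n, where S_all is the running product over recurrences and deaths. The risk set n and the number of recurrences d are the same in both, and S_all cannot exceed S_R. So the Kaplan-Meier figure is never below the cumulative incidence, in any data set.

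**Inputs.**
- Horizon: 5 years (Protocol items 11 and 14).
- Number of patients: 1000 (Protocol item 13), used only for an approximate standard error. The number analysed is not given.
- 5-year local recurrence R, as Kaplan-Meier would estimate it: 2%, 3% or 5% (assumed).
- 5-year mortality D: 5% or 10% (assumed).
- Constant, independent hazards (assumed).

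**Formulas.**
- λ = −ln(1−R)/5 and μ = −ln(1−D)/5
- One minus Kaplan-Meier = 1 − exp(−5λ) = R
- Cumulative incidence = λ/(λ+μ) × [1 − (1−R)(1−D)]
- Complement of local recurrence-free survival = 1 − (1−R)(1−D)
- Approximate standard error = √(R(1−R)/1000)

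**One case in full, R = 3% and D = 10%.** 5λ = 0.03046 and 5μ = 0.10536. The share λ/(λ+μ) is 0.03046/0.13582 = 0.2243. The composite is 1 − 0.97 × 0.90 = 12.70%. The cumulative incidence is 0.2243 × 12.70% = 2.85%. The gap is 3.00 − 2.85 = 0.15 points.

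| R | D | Cumulative incidence | Gap (points) | Standard error (points) | Composite |
|---|---|---|---|---|---|
| 2% | 5% | 1.950% | 0.050 | 0.44 | 6.90% |
| 2% | 10% | 1.899% | 0.101 | 0.44 | 11.80% |
| 3% | 5% | 2.925% | 0.075 | 0.54 | 7.85% |
| 3% | 10% | 2.848% | 0.152 | 0.54 | 12.70% |
| 5% | 5% | 4.875% | 0.125 | 0.69 | 9.75% |
| 5% | 10% | 4.748% | 0.252 | 0.69 | 14.50% |

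The largest gap is 0.252/0.69, or 0.37 of a standard error. Simulation of 4000 registries of 1000 patients with complete follow-up, at R = 3%, gave gaps of 0.074 and 0.152 points (0.14 and 0.27 of the simulated standard deviation) for D = 5% and 10%. Kaplan-Meier was never the lower figure.

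The composite column shows why local recurrence-free survival cannot stand in: at R = 3% its complement is 7.85% or 12.70%, mostly deaths.

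**The case against.** The strongest reply is that nothing is hidden. The SAP states the event rule in one sentence and sets local recurrence-free survival beside the rate. The Protocol asks whether one centre's results can be matched elsewhere, and the share of patients who actually recur is a further question that the reviewer brings. The gap is small, rests wholly on assumed rates and errs against the treatment. The extra estimate would be added after the data were collected and can only equal or lower the reported rate.

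Most of this stands. It rules out calling the plan wrong or contradictory, and it is why the change is optional. It does not remove the gap: the actual probability of recurrence is a natural figure for a quality registry, and the planned oncological estimates do not give it. Labelling the added figure as post hoc answers the last point.

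Three stronger readings are tempting, and the documents do not support them.

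- *That deaths were counted as toxicity events.* The sentence on all Kaplan-Meier estimates could be read that way. But it sits under Oncological Outcome, directly after the oncological endpoints. Toxicity has its own heading and its own event definitions, which a death does not meet, and its planned simple frequencies already show how many patients were affected. Only a one-line clarification is warranted.
- *That the gap becomes material at 10 years.* It would grow with longer follow-up, but the Protocol plans 5 years per patient.
- *That Kaplan-Meier must be kept because the originating centre used it.* The documents cite that centre's publication without saying how its recurrence rate was estimated.

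**Conclusion.** The point holds as a modest improvement to reporting. The local recurrence rate is a Kaplan-Meier net risk with deaths censored, and no planned oncological analysis isolates the actual probability of local recurrence. The direction is certain. The size is not known from the documents: with 2% to 5% recurrence, 5% to 10% mortality and constant independent hazards over 5 years, the overstatement is about 0.05 to 0.25 percentage points, below one standard error at 1000 patients. Higher mortality would widen it. Fewer analysed patients or incomplete follow-up would raise the standard error and make the gap relatively smaller still. It would be wrong to infer that the recurrence results are materially biased or flattering: the bias makes recurrence look slightly worse, and no conclusion is shown to change.

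**What to change.** Keep the Kaplan-Meier local recurrence rate as stated and describe it as having deaths censored. Report beside it an Aalen-Johansen cumulative incidence of local recurrence, with death without recurrence as a competing event, and identify it as added after data collection. Leave the oncological analyses that already count death as an event unchanged. As a separate minor clarification, add one sentence that deaths are not toxicity events in the Kaplan-Meier toxicity rates.

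The cost is two or three sentences and one further analysis of existing data, in software that offers the estimator. The downside is a second, slightly lower post-hoc figure. It depends on mortality and may not be directly comparable with earlier results.
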